An Innovative Mental Health Virtual Ward: Evaluation of Patient-Centred Outcomes**HS26297 (H2024:027)****January 31, 2024**

Introduction

In response to the changes in healthcare systems delivery accelerated by COVID-19 public health restrictions, novel virtual alternatives to in-person care were launched to support the stabilization of individuals in mental health crisis. In Manitoba, Canada, a Virtual Acute Psychiatric Unit (Castillo et al., 2023) and Virtual Crisis Stabilization Unit (Mental Health Virtual Ward; Pullia et al., 2023) were launched early in the pandemic for residents of Winnipeg (the province's largest city) requiring intensive mental health support, as a strategy to divert need for in-person care in hospital and the community-based Crisis Stabilization Unit. After 2 years, the Virtual psychiatric unit closed due to staffing issues, and the Mental Health Virtual Ward continued to operate at 6-'bed' capacity with Government funding. Effective November 2023, these programs have merged and expanded to the entire province as part of a Provincial Virtual Crisis Service that will offer emergency telemental health assessment to rural health centres and intensive follow-up virtual crisis stabilization support post-crisis visit to individuals across Manitoba. The latter program component is referred to as the Mental Health Virtual Ward (MH vWard) with significant potential to increase access to needed care and provide person-centered alternatives to hospital. As this program is unique, long-term outcomes have not been studied. This research proposes to prospectively measure demographic, recovery, service delivery, and systems use outcomes in a cohort of MH vWard admissions, and 2) to establish a cohort of admissions to use as a historical comparison/baseline for more rigorous evaluation in the future.

Background

There is a Need for Accessible Mental Health Crisis Care in Manitoba. Manitoba has the highest prevalence of any mental disorder compared to other Canadian provinces, with major depressive disorder and suicidal ideation being especially prevalent among Manitobans (Palay et al., 2019). Crisis and emergency systems are common entry points to the mental health systems and serve to support individuals with existing mental health difficulties during times of worsening or increased need (Butler et al., n.d.). Winnipeg emergency departments and urgent care centres receive approximately 10,000 visits for mental health concerns yearly, with nearly half of those at HSC alone (Shared Health, 2018). The Crisis Response Centre – open 24 hours a day for individuals to walk-in and receive mental health assessment and support – has over 6000 annual visits and approximately 17,000 calls to the mobile crisis line (Crisis Response Services, 2022). Depending on the level of need, individuals experiencing mental health crises require intervention options ranging from hospital to community systems. Hospital bed shortages and corresponding long ED wait times to admission (upwards of 40 hours in Manitoba; Canadian Institute for Health Information, 2016) have necessitated alternative solutions for those needing higher intensity support.

The virtual units are modelled after inpatient services based on the concept of a Virtual Ward or Hospital-at-home (Arsenault-Lapierre et al., 2021). Intensive daily care is provided remotely to individuals in their own homes or other place of their choosing. Care is delivered by telephone, email, videoconferencing, and text messaging, with daily on-line live hosted groups offered on a topic related to mental wellness and recovery. After hours support is available through a 24-hour a day crisis line and individuals can also access in person support at the Crisis

Response Centre at any time with continuity of care ensured through use of a common electronic patient record. Although the virtual acute psychiatry unit (staffed by psychiatrists and physician assistants) closed after 2 years due to staffing limitations, the Mental Health Virtual Ward has continued to operate 6 “beds” supported by a multidisciplinary team, with approximately 350 admissions/year, and ongoing high demand despite the in-person CSU returning to full capacity in August 2021. The newly expanded province-wide program is a merging of the virtual units, to have a single 12-bed MH vWard that provides multidisciplinary care from a team of clinicians, nurses, and psychiatrists enabling management of a wide range of patients.

Rationale

Further evaluation needs to determine if this novel service is impacting meaningful outcomes (i.e., recovery, functioning, systems use). While systems level outcomes such as avoided emergency department visits and hospitalization are often prioritized by decision makers and researchers, they may not be the only or most meaningful outcomes for patients and families (dosReis et al, 2022; Frank et al., 2014). For example, in previous work done by the PI on the impact of a post-discharge transitional program for patient with mood and anxiety disorders, it was discovered that many of the components of the planned program either didn’t work or didn’t matter to patients and families (Bhattacharyya et al, 2015). Identifying the most meaningful outcomes for both the systems and the patients, and evaluating if the MH vWard is having a positive impact on these outcomes is critical to inform ongoing improvement and to make sure that the care is meeting the needs of the people who receive it in the best way possible. We also need to evaluate this program to support ongoing investment in the resources needed to run it, and to support its scale and spread.

Objectives

The objectives of this project are to: (1) prospectively measure demographic, recovery, service delivery, and systems use outcomes in a cohort of MH vWard admissions, and (2) establish this cohort for use in future research.

Methods

Study Design

Objective 1 involves the prospective collection of data from a cohort of MH vWard admissions over approximately 1 year to measure demographic, recovery, service delivery, and systems. Outcomes for consenting individuals will be assessed at time of admission (Time 1), 1 week after discharge (Time 2), 4 weeks after discharge (Time 3), and 6 months after discharge (Time 4). Data on health systems use during the 3 months prior to admission (i.e., pre-test data) and 6 months after admission will be collected in order to identify changes in post-intervention systems use. Within the prospective cohort study, we will also establish the requirements for the cohort to be used for future research (Objective 2).

Patient and Caregiver Advisory Committee (PCAC). This study includes a PCAC who will be involved in the initial selection of outcomes and will give input into the overall study procedures to incorporate the voices of people with lived experience. Given that this study

collects data from individuals experiencing a mental health crisis, the input from a PCAC will be essential to determine optimal data collection protocols that increase recruitment and retention and overall data quality. The PCAC will consist of approximately 6 individuals/caregivers from across Manitoba who have lived experience with crisis services. The PCAC will meet regularly with the study team to achieve project objectives. Oversight of the PCAC will be through our patient engagement lead and partnership with Peer Connections Manitoba.

Exposure to Intervention

Individuals referred to the MH vWard receive an intensive level of daily support that approximates what would be provided through receipt of in-person services but they remain in the community, usually at their own homes or with family/friends. Care in the MH vWard is delivered by any combination of telephone, email, videoconferencing, and text messaging. Individuals have the option of opting in to the use of a web- or app-based tool to complement their care delivery and support self-management. The typical duration of admission is 5 days with flexibility based on individual needs. The program is 'open' 8am to 10pm. All individuals develop an after-hours crisis plan that varies depending where they are located and what the local resources are.

Program components are as follows:

Individual therapy and care planning. Daily 1:1 sessions with a clinician or psychiatry team member to assess and monitor, develop and progress on recovery goals, discuss referrals, etc.

Engagement of formal and informal supports. Direct and indirect communication with community providers for collateral and collaboration, as well as involvement of informal supports (i.e. family, friends) through engagement during 1:1 sessions or additional contacts.

Medication reconciliation and management. Full medication review and reconciliation with program nurse at time of admission. Psychiatry team will manage medications during stay if relevant. Discharge medication reconciliation is completed when appropriate.

Group programming. Daily on-line, live hosted groups are provided for all individuals admitted. These will cover a range of content including skills from Cognitive Behavioural Therapy, medication education, etc.

Referrals for follow-up services. Referrals to community-based services for ongoing support post-discharge.

After hours support. All individuals will create their own individualized after hours support plan at the time of referral and/or intake. Depending where the individual resides this will include crisis lines, in person options, etc.

Telus Home Health Monitoring (HJM) App. At intake, individuals may opt in to using the Telus HJM app which is custom designed to complement the services provided by the program. This system has been approved and adopted by Shared Health for the remote home monitoring of patients. The app pushes periodic surveys to admitted individuals that prompts them to track symptoms and monitor their progress, select availability for 1:1 support and group programming, and work through their crisis plan if needed. The app also allows the custom selection of educational resources that the individual can reference as part of their

treatment plan. Alerts can be sent to the clinical team based on any pre-determined criteria that the team identifies (e.g. a symptom score above a certain threshold). The clinical team has access to a dashboard through which an individual's use of the app is monitored during program hours. Individuals are active on the app for the duration of their admission; after which they retain access to the materials for an additional 30 days but no longer are monitored by the clinical team.

Integration with in-person services. In the case that an admitted individual requires their care to step up to in-person, the MH vWard is integrated with emergency services and inpatient units. Whenever possible, individuals are admitted directly from their home to the inpatient unit to avoid an intermediate emergency visit. If needed due to acute safety or other concerns, local emergency services (911, RCMP) are activated and the team communicates directly with the receiving site to ensure continuity of care.

Participants

Eligibility

All individuals admitted to the virtual ward during the study period are eligible for participation in the study. There are no exclusion criteria.

Sample Size

A sample size calculation was made based on the change score (paired t-test) of the study's primary outcome measure for recovery (WHO-5 Well-being Index). The minimum clinically significant difference for the WHO-5 Well-being Index has been established (Topp et al., 2015). Parameter information for the power calculation was provided by a study that used the WHO-5 Well-Being Index in a psychiatric inpatient population (Newnham et al., 2010). The estimated standard deviation of the change score for the present study was determined to be 4.9 based a standard deviation of 5.5 and a r_{within} of 0.6. Additional parameters included a two-tailed test at $\alpha=0.05$, a type II error rate of 20%, and a medium to large effective size of 0.65. Based on these parameters, the required sample size is 452.

Drawing on Mental Health Virtual Ward admission statistics in the 2022 calendar year, based on the 6-bed unit, there were about 350 admissions. With the program growing to 12 beds, it is expected the total number of admissions would double to 700 over 1 year. We anticipate about 10-15% of individuals may choose not to participate in the study so we are expecting a sample of around 595 admissions. With participant incentives (gift cards) for responding to surveys and follow up contacts by our team, we hope for an 80% response rate for outcome surveys based on completion rates described by Gilbody et al. (2015) who used a similar method for retention in a trial of an on-line mental health intervention. We estimate that this would result in outcome data at Time 2 for 476 admissions with complete pre and post data over 1 year. Recruitment could be extended by several months if we are failing to meet targets within the 1-year timeframe.

Recruitment

Recruitment script at time of referral & Referral Confirmation/Welcome Email

The recruitment process begins with a welcome email that is sent by the program. From here, interested individuals may click on a link in the referral confirmation/welcome email and self-proceed to review the online consent form and enroll in the study. For those who do not complete this step prior to their admission intake (typically 24-48 hours from receipt of referral), a clinician will follow up to inquire about their interest during this meeting. Those indicating interest at that point will be directed to the same information via email. For those with no email address, permission will be obtained from patients by a clinician for a research team member to reach out for the purposes of discussing the study and enroll over the phone. The first month of the study will be a feasibility period to test out our recruitment strategies. The researchers will seek feedback and suggestions to troubleshoot recruitment barriers from the clinical team members and the PCAC during this time. Recruitment strategies will be adjusted as required.

Data Collection

Data will be collected through self-report surveys at designated time points, as well as chart review to collect service delivery and healthcare utilization data.

Participant Incentives. Participants will be offered honoraria as incentives for study participation. Participants will be offered \$5 gift cards at each follow-up data collection time points (Time 2, 3, and 4). Gift cards will be administered electronically (unless physical cards are requested) by the RA.

Variables & Data Sources/Measures

Variables of interest for the study include participant demographics, along with service delivery, recovery, and systems use outcomes.

Demographic Variables (Time 1). The Demographic Questionnaire and SINCERE questionnaire will be completed at Time 1 (admission). The demographic questionnaire will include variables related to sociodemographic information: age, gender, education, income, employment status, relationship status, living situation, urban/rural residence, race/ethnicity, and clinical reason for referral/diagnosis. The data will be collected from participant self-report.

Recovery Outcomes (Time 1, 2, 3, and 4). Recovery will be measured using 2 questionnaires that were co-selected with input from the PCAC: the **WHO-5 Well-Being Index** and the Maryland Assessment of Recovery Scale- 12 item (MARS-12). The Who-5 Well-Being Index is a 5-item measure that assesses subjective psychological well-being" (Topp et al., 2014, p. 167). It has been used to monitor global recovery among psychiatric inpatients showing good sensitivity to change with an established MCID that correlates to other validated measures of psychiatric impairment (Topp et al., 2014). MARS-12 is a shortened version of the MARS-24 designed to measure recovery orientation among individuals with mental illness (Drapalski et al., 2012).

Service Delivery Outcomes (Discharge). Service delivery outcome data are: length of stay, and outcome of stay (discharge, transfer to in person CSU/hospital, emergency activation, and lost

to follow-up. These data will be provided by the clinical team lead as a report approximately monthly.

Systems Use Outcomes (Time 1, 2, 3, 4). Systems use outcomes will include: CRC use, Emergency Department use, and psychiatric hospitalizations. We will collect both self-report and health administrative data to assess for recall bias and to enable some systems use outcomes for individuals who are lost to follow-up in the study. At baseline, systems use in the 3 months prior to admission will be collected. At time 1 and 2, we will collect systems use since discharge from the MH vWard. At time 4, we will collect prior 1-month utilization, including if they utilized the MH vWard again during that time period. Self-report systems variables will be collected using a modified version of the Service Utilization based on the **Client Service Receipt Inventory (CSRI)**. Corresponding health administrative data will be extracted from the electronic medical records of participants by a research team member. Reliable health administrative data will only be available for Winnipeg-based participants as few rural health care facilities utilize the available electronic medical records (most are paper-based).

Time Points

Data will be collected at 4 different time points:

Time 1 (baseline):

- Participants are to complete baseline questionnaires within 72 hrs of admission
- If a participant does not complete questionnaires within 72 hrs of admission, the participant will be excluded from further data collection.

Time 2 (primary outcome):

- Participants are administered questionnaires 1 week AFTER discharge, with + 1 week of leeway for completion (within 7-14 days of discharge).

Time 3 (secondary outcome):

- Participants are administered questionnaires 5 weeks AFTER discharge, with +/- 1 week of leeway for completion (within 4-6 weeks of discharge).

Time 4 (secondary outcome):

- Participants are administered questionnaires 6 months AFTER discharge, with a +/- 2 weeks of leeway for completion (within 6 months -2 weeks and 6 months +2 weeks).

	Time 1 (admission)	Discharge	Time 2 (1 week post discharge)	Time 3 (5 weeks post discharge)	Time 4 (6 mos post discharge)
Demographic data (Demographic Questionnaire; SINCERE)	X				
Recovery outcomes (WHO-5,	X		X	X	X

MARS-12; Global Recovery Questions)					
Service Delivery outcomes (Data capture sheet)		X			
Systems use outcomes (Service Utilization; data capture sheet)	X		X	X	X

- For self-report surveys at Time 1, 2 and 3, data may be collected through the Telus HHM App as they will also be utilized for assessment and care planning purposes (for those utilizing the App as part of their care), RedCap (for those not utilizing the App), or by phone or in person, for those with this preference or who lack an email/internet connection. All participants will complete questionnaires at Time 4 on REDCap.

Participants completing questionnaires electronically (Telus, REDCap) will receive up to 2 reminders by phone or email at Time 2, 3, and 4, if needed.

Participants completing questionnaires over the phone or in person with the RA will receive up to 2 phone calls to connect for the purpose of completing the questionnaire together.

All data entered into the Telus HHM App for consenting participants will be output in an electronic report by a clinical team member and shared with the research team. The research team member will then manually enter these responses into the REDCap survey.

Data Storage

Clinicians will upload PDF reports containing questionnaire responses generated from the Telus App into a shared folder on the Shared Health Network drive, accessible by the PI. The PI will generate hard copies of the reports for the RA to extract the data from. Once data are manually entered into REDCap and verified, hard copies will be destroyed using confidential shredding. All responses will be stored in REDCap along with identifying data and consent information.

Statistical Analyses

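### The required sample size of 452 does not follow from a standardised effect of 0.65, which needs 21 pairs; it matches 0.65 taken as a raw point difference (standardised effect about 0.13)

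*Combined protocol and SAP*

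**What the plan says.** The calculation is in the combined protocol and SAP, under Participants, Sample Size. It is a paired t-test on the change in WHO-5, the primary recovery measure. The plan reports a "standard deviation of the change score for the present study was determined to be 4.9 based a standard deviation of 5.5" and a within-person correlation of 0.6. It adds a two-tailed alpha of 0.05, a 20% type II error rate and a "medium to large effective size of 0.65. Based on these parameters, the required sample size is 452". No unit is attached to 0.65, and no target difference in WHO-5 points is given.

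Non-response is handled in the next paragraph, separately from the 452. About 700 admissions are expected, 595 after refusals, and an 80% response rate then gives "outcome data at Time 2 for 476 admissions with complete pre and post data over 1 year". The section closes with: "Recruitment could be extended by several months if we are failing to meet targets within the 1-year timeframe".

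**The concern.** An effect size described as medium to large is normally a standardised one, and a paired comparison with an effect of that size needs a few dozen pairs at most. A requirement of 452 implies a much smaller effect. Either the number or its description must therefore be wrong.

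This is the only power justification the plan gives for its primary outcome. Taken at its label, 0.65 means a mean change of about 3.2 points (0.65 × 4.919). Taken as the number that yields 452, it means a change of 0.65 points. The two targets have very different implications for what a statistically significant change would show. The required figure may also have an operational role. The plan expects 476 pairs against 452, a margin of 24, and allows recruitment to be extended if targets are missed. It does not say whether 452 is one of those targets.

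**Working it through.** **Inputs, all from the Sample Size section.** SD 5.5; within-person correlation 0.6; change SD stated as 4.9; two-sided alpha 0.05; power 0.80; effect 0.65; stated requirement 452.

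**Step 1: change SD.** SD of change = √(2 × 5.5² × (1 − 0.6)) = 5.5 × √0.8 = 4.919. This agrees with the printed 4.9.

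**Step 2: method.** For a paired t-test with standardised effect dz (mean change divided by SD of change), power comes from the noncentral t distribution with n − 1 degrees of freedom and noncentrality dz√n. The required n is the smallest that gives power of at least 0.80. The normal approximation, n ≈ (1.960 + 0.842)² / dz² = 7.849 / dz², serves as a check.

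**Step 3: the plan's figure with 0.65 as a standardised effect.** With dz = 0.65, the normal approximation is 7.849 / 0.4225 = 18.6. The exact calculation gives n = 21 (power 0.809; n = 20 gives 0.787). The stated 452 is not reproduced and is about 21.5 times larger (452 / 21).

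**Step 4: the plan's figure with 0.65 as a raw difference.**
- Unrounded SD: dz = 0.65 / 4.919 = 0.1321. The normal approximation is 449.6. The exact calculation gives n = 452 (power 0.8004; n = 451 gives 0.7996), an exact match.
- Printed SD: dz = 0.65 / 4.9 = 0.1327. The exact calculation gives n = 448.

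**Step 5: other readings of 0.65 as a standardised effect.**

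| Reading | n |
|---|---|
| 0.65 scaled to the SD of 5.5 (dz = 0.65 × 5.5 / 4.919 = 0.727) | 17 pairs |
| One-sided test | 17 pairs |
| 90% power | 27 pairs |
| 21 pairs inflated for 20% dropout (21 / 0.8, rounded up) | 27 |
| Alpha divided over three follow-up times (0.05 / 3) | 28 pairs |
| 95% power | 33 pairs |
| Two independent groups, d = 0.65 (39 per group) | 78 in total |

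None is near 452. Attrition cannot close the gap either, because the plan applies it afterwards: 700 × 0.85 = 595, then 595 × 0.80 = 476.

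**Step 6: what the stated numbers deliver.**
- The change detectable with 80% power is 0.65 points (dz = 0.132) at 452 pairs and 0.63 points (dz = 0.129) at 476.
- Power for dz = 0.65 at 452 pairs is above 0.999.
- The 95% confidence interval half-width for the unadjusted mean change, t × 4.919 / √n, is 0.455 points at 452 pairs and 0.443 at 476.

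**The case against.** The strongest reply is that N was not miscalculated. Every printed number reproduces 452 to the last digit once 0.65 is read as a difference in points, so the fault would be one of labelling. That reading is very likely, and it should be the sponsor's first check. It does not rescue the paragraph. The plan never expresses 0.65 in points, and on this reading the descriptor is wrong, because the standardised effect is about 0.13. It also remains open whether a 0.65-point change was the intended target or whether a standardised 0.65 was entered in the wrong field.

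A second reply is that little depends on it. This is a single cohort taking all consenting admissions over about a year. One of its objectives is to establish the cohort for later research, and power for 0.65 SD is ample. That is true, and it limits the harm: no analysis or participant count has to change. But the plan presents 452 as a requirement derived from stated parameters, and as labelled they do not produce it.

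Two limits on the argument are also fair. The ratio of the labelled effect to the implied one (0.65 / 0.132 = 4.9) is simply the change SD, so it restates the units problem and is not further evidence. And the documents cite a minimum clinically significant difference without printing its value, so nothing here shows whether 0.65 or 3.2 points is clinically adequate.

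**Conclusion.** The concern holds. As labelled, the parameters require 21 pairs, not 452. The stated 452 corresponds to a raw change of 0.65 points, a standardised effect of about 0.13. The result assumes the plan's own SD of 5.5, correlation of 0.6, two-sided alpha of 0.05 and 80% power, and a paired t-test on complete pairs. Points are on whatever WHO-5 scoring the SD of 5.5 refers to. The raw-difference explanation is inferred from an exact numerical match and is not stated in the documents, which do not settle whether 0.65 or 452 reflects the intent. The study is not underpowered for a standardised effect of 0.65. The error is in the stated justification, which should be corrected because it is the only power basis given for the primary outcome.

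**What to change.** Restate the calculation with units, after checking the original power computation to see which quantity was entered. Either version would do:

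- **(a)** 452 complete pairs give 80% power, at two-sided alpha 0.05, for a mean WHO-5 change of 0.65 points (change SD 4.92, standardised effect about 0.13). Delete the medium-to-large descriptor.
- **(b)** A standardised effect of 0.65 needs 21 complete pairs. The one-year cohort is then justified by the cohort objectives and, if the sponsor wishes, by precision: a 95% confidence interval half-width of about 0.45 points at 452 pairs and 0.44 at the expected 476. These half-widths are for the unadjusted change, whereas the planned analysis is a covariate-adjusted repeated-measures model, so they should be labelled as approximate.

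If 452 is a target that could trigger extended recruitment, say so and give its corrected basis.

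The cost is one paragraph of protocol wording, with no extra participants, data or analyses. Under (a) the target effect reads as small; under (b) the cohort size must be defended on grounds other than power.

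### The systems-use recall windows cannot be applied as written, and they do not deliver the stated 6-month post-admission window for participants without reliable charts

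*Combined protocol and SAP*

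**What the plan says.** All of these statements are in the combined protocol and SAP.

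- **Study Design** gives the overall window: "Data on health systems use during the 3 months prior to admission (i.e., pre-test data) and 6 months after admission will be collected". The stated purpose is to identify change in use after the intervention. The same section defines Time 1 as admission and puts the third survey at "4 weeks after discharge (Time 3").
- **Variables & Data Sources/Measures** heads the item "Systems Use Outcomes (Time 1, 2, 3, 4"). It gives baseline a look-back over the 3 months before admission. It then says "At time 1 and 2, we will collect systems use since discharge from the MH vWard", and "At time 4, we will collect prior 1-month utilization". No sentence gives a recall window for Time 3.
- The same paragraph says that corresponding administrative data will be extracted from electronic records, and that these are reliable only for Winnipeg-based participants. No extraction period is given there.
- **Time Points** places Time 2 at days 7 to 14 after discharge. For Time 3 it says "Participants are administered questionnaires 5 weeks AFTER discharge, with +/- 1 week of leeway for completion (within 4-6 weeks of discharge"), and for Time 4 "Participants are administered questionnaires 6 months AFTER discharge, with a +/- 2 weeks of leeway for completion". Its table marks systems use at all four time points.
- **Exposure to Intervention**: "The typical duration of admission is 5 days with flexibility based on individual needs".
- **Statistical Analyses** gives no model for systems use. Secondary outcomes are to be handled by methods like those for the primary outcome, according to variable type.

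**The concern.** Three statements about one outcome do not fit together. A since-discharge question cannot be asked at admission. A scheduled survey (Time 3) has no recall period. The last survey looks back one month, while the design section states a continuous 6 months.

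Systems use is one of the outcomes named in Objective 1, and the plan wants a before-and-after comparison of it. Whoever builds the questionnaire and the extraction form must know which days each item covers. Days that are not asked about cannot be reliably recovered later for participants without usable electronic records. The Introduction says the programme now serves the whole province, so such participants are expected in the cohort.

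The windows also differ in length: 3 months at baseline, one or two weeks at Time 2, up to six weeks at Time 3 (once corrected) and one month at Time 4. No common scale for comparing them is stated.

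**Working it through.** The plan gives no figure for this gap, so there is none to reproduce. The check is date arithmetic on the plan's own windows.

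**Inputs**, in days after discharge
- Time 2: 7 to 14 (Time Points).
- Time 3: 5 weeks ± 1 week = 28 to 42 (Time Points).
- Time 4: 6 months ± 14 days (Time Points), with a 1-month look-back (Systems Use Outcomes).
- Assumptions: 6 months = 182 days, 1 month = 30 days, every survey completed.

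**Label read as Times 2 and 3**

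Gap = (Time 4 day − 30) − Time 3 day.
- Shortest: (182 − 14 − 30) − 42 = 96 days.
- Nominal: (182 − 30) − 35 = 117 days.
- Longest: (182 + 14 − 30) − 28 = 138 days.

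As shares of 182 days these are 96/182 = 53%, 117/182 = 64% and 138/182 = 76%.

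**Sensitivity to day counts.** With 6 months as 180 to 184 days and 1 month as 28 to 31 days, the shortest gap is 93 to 100 days and the longest is 135 to 142 days. With 183 and 30 days the range is 97 to 139.

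**Label read literally** (no recall window at Time 3)

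Gap = (Time 4 day − 30) − Time 2 day.
- Shortest: (182 − 14 − 30) − 14 = 124 days.
- Nominal: (182 − 30) − 7 = 145 days.
- Longest: (182 + 14 − 30) − 7 = 159 days.

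**Does the gap lie inside the stated window?** That window runs from admission. With the typical 5-day stay it ends on day 182 − 5 = 177 after discharge. The latest start of the Time 4 look-back is day 182 + 14 − 30 = 166, so the whole gap falls inside it. The 5 days of the stay are also in no self-report window, because baseline ends at admission and follow-up recall starts at discharge. The outcome-of-stay report does record transfers and emergency activations during the stay.

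**Time 3 at 4 weeks or 5 weeks.** The nominal gap is 182 − 30 − 28 = 124 days at 4 weeks and 117 at 5 weeks, a shift of 7 days. Both lie within 96 to 138.

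**Charts.** Two readings are open. If extraction follows the Study Design window, charts cover the gap for Winnipeg-based participants. If corresponding means the same periods as the surveys, the gap is in the charts too. The Time Points table lists the data capture sheet beside the survey at Times 1 to 4, which allows the second reading. Study Design supports the first.

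**The case against.** The strongest reply is that Study Design does not say the 6 months will come from self-report. Data Collection assigns utilization data to chart review as well as surveys, so a one-month question can coexist with 6-month extraction. The Winnipeg limit is disclosed, and charts are said to enable only some outcomes for people lost to follow-up. The questionnaire and data capture sheet are not among the documents, and their wording could settle the Time 3 window and the extraction period. A short recall at Time 4 is also a defensible choice in a plan that is concerned about recall bias.

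Much of this stands, and it rules out several stronger readings that a reader might infer.
- *The 6-month window fails for everyone.* Not supported, since charts may deliver it for Winnipeg-based participants.
- *A continuous 6-month chart record is assured for Winnipeg-based participants.* Not supported either, since the extraction period is left open.
- *One-month recall at Time 4 is itself an error.* It is not. The fault is the mismatch with the stated window.
- *Raw counts over unequal periods will be compared.* The plan does not say so. It only omits a common scale.
- *The main result is affected.* The primary outcome is the WHO-5, and the sample size of 452 rests on it.

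The reply does not remove the impossible instruction for Time 1, the missing Time 3 window, or the unqualified 6-month statement. Disclosing the Winnipeg limit in one section does not amend the general statement in another.

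**Conclusion.** The point holds for a secondary outcome and should be fixed. The collection rule cannot be followed as written at Time 1 and is missing at Time 3. For participants without reliable charts, the stated 6 months after admission are not delivered.

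With the label corrected, the unasked period is about 96 to 138 days. With the literal wording it is about 124 to 159 days. These figures assume 182 or 183 days for 6 months, 30 days for 1 month and complete surveys. Missed surveys lengthen the gap, and the plan hopes for an 80% response.

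Reading the label as Times 2 and 3 is an inference, though a natural one, because baseline has its own window and Time 3 otherwise has none. The documents give no split between Winnipeg and other participants, so the affected share is unknown. Confidence is high on the textual conflict and lower on what the unseen forms may already settle.

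**What to change.** 1. In Systems Use Outcomes, change the label to Time 2 and Time 3. State the Time 3 recall window so that use already reported at Time 2 is not counted twice. Reconcile the 4-week timing in Study Design with the 5-week timing in Time Points.
2. State that chart extraction covers the full Study Design window, 3 months before and 6 months after, with one anchor used throughout.
3. Qualify Study Design so that the continuous 6-month before-and-after comparison is claimed only for participants with reliable charts. For the others, report only the periods asked about, and give their share of the cohort.
4. In Statistical Analyses, compare systems use as rates per observed person-time, reported by data source, because the windows differ in length.

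The cost is wording edits in these sections, a record of who has reliable charts, and one analysis paragraph. No survey or visit is added. The real price is a narrower claim: the 6-month comparison would describe the Winnipeg-based part of a province-wide programme. Lengthening the Time 4 recall would reduce the gap but trades coverage against recall error, so it is not part of this fix.
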